## 1 INTRODUCTION

This Statistical Analysis Plan (SAP) describes the methodologies, rules, and conventions to be used in the presentation and analysis of the efficacy, safety, and pharmacokinetics (PK) for Protocol ISIS 678354-CS8.

The analyses described in this SAP are based upon the following study documents:

- Study Protocol (Amendment 2: Mar 22, 2023)
- electronic Case Report Form (eCRF) (Sep 26, 2023)

Revision(s) of this SAP will not be required for any subsequent amendments to the protocol which do not change the analyses described in this SAP. The SAP will be finalized prior to database lock (DBL). If circumstances should arise during the study rendering this analysis inappropriate, or if improved methods of analysis should arise, updates to the analyses may be made. Any deviations from the SAP after DBL, reasons for such deviations and all alternative or additional statistical analyses that may be performed, will be documented in the final clinical study report.

## 2 STUDY OBJECTIVES

### 2.1 Primary Objective

To evaluate the effect of olezarsen on percent change in fasting triglyceride (TG) levels compared to placebo.

### 2.2 Secondary Objectives

To evaluate the effect of olezarsen as compared to placebo on:

- Percent change in fasting TG levels upon longer duration of treatment (1 year)
- Proportion of patients who achieve different thresholds in fasting TG levels
- Percent change in fasting apolipoprotein C-III (apoC-III), very low-density lipoprotein cholesterol (VLDL-C), remnant cholesterol, non-high-density lipoprotein cholesterol (non-HDL-C), high-density lipoprotein cholesterol (HDL-C), total cholesterol (TC), apolipoprotein B (apoB), low-density lipoprotein cholesterol (LDL-C), and apolipoprotein A-1 (apoA-1)
- Adjudicated acute pancreatitis event rate in patients with  $\geq 2$  events of adjudicated acute pancreatitis in 5 years prior to enrollment
- Adjudicated acute pancreatitis event rate

### 2.3 Exploratory Objectives

To evaluate the effect of olezarsen on the incidence of major adverse cardiovascular events (MACE)

### 2.4 Safety and Tolerability Objective

To evaluate safety and tolerability of olezarsen

### 2.5 PK Objective

To evaluate PK of olezarsen

### 3 INVESTIGATIONAL PLAN

#### 3.1 Overall Study Design and Plan

The 678354-CS8 study is a multi-center, randomized, double-blind, placebo-controlled trial done in conjunction with the TIMI Study Group, an academic research organization based at Brigham and Women's Hospital and Harvard Medical School. Eligible patients will enter an approximately 4-week Screening Period (that may be extended to 8 weeks if assessments can't be completed within the 4-week period) that includes an at least 2-week Diet/ life-style Stabilization/Run-in Period, and an approximately 2-week Qualification Period. Following Qualification, approximately 152 eligible patients will be randomized 1:1 to Cohort A (50 mg) or Cohort B (80 mg) and each cohort further randomized 3:1 to receive olezarsen or placebo in a 53-week Treatment Period. Patients in Cohort A will receive 50 mg of olezarsen once every 4 weeks (Q4W) or matching volume of placebo (0.5 mL) during Weeks 1-49 of the Treatment Period. Patients in Cohort B will receive 80 mg olezarsen once Q4W or matching volume of placebo (0.8 mL) during Weeks 1-49 of the Treatment Period. The 80 mg once Q4W may be adjusted to 50 mg once Q4W due to tolerability or safety reasons at any point during the study following consultation with the Sponsor Medical Monitor or designee. Randomization will be stratified by Qualification fasting TG levels of < 500 mg/dL vs  $\geq$  500 mg/dL. Following the Week 53 visit, patients will enter the 13-week Post-Treatment Follow-up Period. All endpoints will be evaluated after the last patient has completed the Week 53/early termination (ET) Visit.

#### 3.2 Study Endpoints

##### 3.2.1 Primary Endpoint

Percent change in fasting TG from Baseline at Month 6 (average of Weeks 25 and 27) compared to placebo.

##### 3.2.2 Secondary Endpoints

- Percent change in fasting TG from Baseline at Month 12 (average of Week 51 and Week 53) compared to placebo.
- Proportion of patients who achieve fasting TG < 150 mg/dL (1.69 mmol/L) at Month 6 and proportion of patients who achieve fasting TG < 150 mg/dL at Month 12 compared to placebo in the subgroup of patients with baseline fasting TG < 500 mg/dL (5.65 mmol/L).
- Proportion of patients who achieve fasting TG < 500 mg/dL (5.65 mmol/L) at Month 6 and proportion of patients who achieve fasting TG < 500 mg/dL at Month 12 compared to placebo in the subgroup of patients with baseline fasting TG  $\geq$  500 mg/dL.
- Percent change in fasting apoC-III, VLDL-C, remnant cholesterol, non-HDL-C, HDL-C, TC, apoB, LDL-C, and apoA-1 from Baseline at Month 6 and at Month 12 compared to placebo.
- Adjudicated acute pancreatitis event rate during the Treatment Period compared to placebo in patients with  $\geq$  2 events of adjudicated acute pancreatitis in 5 years prior to enrollment
- Adjudicated acute pancreatitis event rate during the Treatment Period compared to placebo

### 3.2.3 *Exploratory Endpoints*

- Events rates of independently adjudicated MACE.
- Additional analyses of the broader MACE composite of CV death, non-fatal MI, non-fatal ischemic stroke, or arterial revascularization (coronary or non-coronary)
- The triple composite of CV death, non-fatal MI, and non-fatal ischemic stroke and its individual components (CV death; MI; ischemic stroke) may be performed depending on rates of MACE.

### 3.2.4 *Safety and Tolerability Endpoints*

Safety and tolerability assessments include adverse events (AEs), vital signs and weight, physical examinations, clinical laboratory tests, electrocardiogram (ECG), and use of concomitant medications. Safety and tolerability results in patients receiving olezarsen will be compared with those receiving placebo.

### 3.2.5 *PK Endpoints*

Plasma trough and post-treatment concentrations of olezarsen, and potential exposure/response relationship for apoC-III and TG.

## 4 STATISTICAL METHODOLOGY

### 4.1 Data Management and Quality Assurance

#### 4.1.1 *Central Laboratory Data*

Ionis Pharmaceuticals, Inc. (Ionis) and Medpace are responsible for the format of the laboratory electronic data transfers and the transfer schedule. Central laboratory data results are not stored in the EDC system. Medpace and Ionis are responsible for the review of the clinical laboratory data. This process involves reviewing the patient and visit identifiers in the central laboratory data results against the central lab data identifiers collected in the EDC system. Investigator sites have access to the data via lab reports sent directly from the laboratory or through the laboratory's web portal (in which case Investigators only have access to data from their site).

The patients, Investigators, study staff, and the Sponsor are to remain blinded to central and local lipid data (TG, apoC-III, TC, HDL-C, remnant cholesterol, apoB, VLDL-C, non-HDL-C, LDL-C, and apoA-1) starting after the first dose on Day 1 then throughout the remainder of the study or as noted for TG or apoB alerts per Section 8.5.7 of the study protocol.

#### 4.1.2 *Pharmacokinetic Data*

Ionis is responsible for the management and review of the PK data. This process involves reviewing the patient and visit identifiers with the clinical data collected in the EDC system. The PK data are not stored in the EDC system. Prior to unblinding of the final analysis, any PK concentration datasets provided to Ionis by the bioanalytical lab will be provided without reference to actual patient identifiers to avoid inadvertent or accidental unblinding. The bioanalytical lab may provide Ionis with datasets containing dummy patient identifiers unrelated to the actual identifiers to allow review of the PK data.

#### 4.1.3 *Adjudicated Data*

All AEs and serious AEs (SAEs) that occur during the study that are consistent with an event of acute pancreatitis will be adjudicated by a blinded, independent committee according to the Atlanta classification of acute pancreatitis ([Banks et al. 2013](#)) and as outlined in the Acute Pancreatitis Adjudication Charter (PAC). In addition, data for episodes of acute pancreatitis or suspected pancreatitis in the 5 years prior to enrollment will be collected by review of each patient's medical chart and these events will also be adjudicated.

All AEs and SAEs that occur during the study that are consistent with a MACE will be adjudicated by a blinded, independent MACE-Adjudication Committee (MACE-AC) as outlined in the MACE Adjudication Charter.

The MACE-AC will adjudicate all fatal events and events suggestive of non-fatal myocardial infarction, hospitalization for unstable angina, hospitalization for (worsening) heart failure, coronary or non-coronary revascularization procedures, or stroke. The criteria used by the MACE-AC to determine the occurrence of any of the events will follow the recommendations included in published Cardiovascular and Stroke Endpoint Definitions for Clinical Trials ([Hicks et al. 2018](#); [Thygesen et al. 2018](#)).

## 4.2 General Considerations

### 4.2.1 *Data Presentation*

Descriptive summary statistics including the number of subjects with non-missing data (n), mean, median, standard deviation (SD), standard error of mean (SEM), interquartile range (25th percentile, 75th percentile), and range (minimum, maximum) for continuous variables, and counts and percentages for categorical variables will be used to summarize most data. The minimum and maximum will be reported to the same number of decimal places as the raw data recorded in the database. The mean, median, lower quartile and upper quartile will be reported to one more decimal place than the raw data recorded in the database. The SD and SEM will be reported to two more decimal places than the raw data recorded in the database. In general, the maximum number of decimal places reported shall be four for any summary statistic.

Categorical data will be summarized in terms of n, frequency counts and percentages. Percentages will be rounded to one decimal place unless it is an integer. Percentages will not be presented for zero counts.

Changes from baseline in categorical data will be summarized using shift tables where appropriate.

All statistical tests will be conducted using 2-sided tests with 5% Type 1 error rates unless otherwise stated. Where appropriate, p-values will be reported. P-values greater than or equal to 0.0001, in general, will be presented to four decimal places. P-values less than 0.0001 will be presented as "< 0.0001".

Confidence intervals (CIs) will be presented to one more decimal place than the raw data.

The primary endpoint will be assessed on the Full Analysis Set (FAS) and Per Protocol Set (PPS), with the former being the basis for the primary efficacy analysis. All the secondary endpoints will be assessed on the FAS. All safety assessments will be performed on the Safety Set. PK endpoints will be assessed in the PK Set as applicable.

Efficacy and safety results will be summarized under the treatment to which patients are randomized. For safety results, should there be any cases after unblinding in which a patient received treatment other than what was randomized, such cases will be discussed and noted in footnotes where applicable.

The efficacy summaries will be presented by the treatment group (placebo, olezarsen 50 mg, olezarsen 80 mg). The disposition, demographics, baseline characteristics, medical history, prior and concomitant medications, and protocol deviations will be presented by treatment group, total olezarsen treated (50 mg + 80 mg) and overall. The safety data will be presented by the treatment group and total olezarsen treated.

All tables and figures containing efficacy endpoints will indicate whether they present raw data or adjusted results from the statistical model, with footnotes indicating the model used and covariates included in the model.

Selected safety endpoints will be analyzed using below analysis method:

- The crude incidence rates, risk difference with 95% CI between each active treatment group (or total olezarsen treated) and pooled placebo group. The crude incidence rate (in percentage) is defined as the number of patients who experienced at least one event times 100 divided by the total number of patients. The 95% CI of risk difference in crude incidence rate will be estimated using the unstratified Miettinen-Nurminen (MN) method.
- Exposure-adjusted incidence rate (EAIR) rates, EAIR difference with 95% CI between each active treatment group (or total olezarsen treated) and pooled placebo group. EAIR is defined as the number of patients who experienced at least one event times 100 divided by total person-years at risk for the event. For patients with events, the time at risk is the time from the first dose date to the first onset of an event (i.e., first event date minus first dose date plus one day divided by 365.25); for patients with no event, the time at risk is the total duration in the on-study period in year (i.e., last participation date or data cutoff date minus first dose date plus one day divided by 365.25). The difference of EAIR and 95% CI will be estimated using Wald's method.
- Exposure-adjusted event rate (EAER), defined as the number of events times 100 divided by the total duration in the on-study period in year.

All tables, figures and data listings to be included in the report will be independently checked for consistency, integrity and in accordance with standard Medpace (a CRO that is responsible for pre-programming datasets and TLFs for the Study) procedures.

Missing visits or missing data related to COVID-19 may be listed. Additional listings may be provided for all patients impacted by COVID-19 during conduct of the study. Additional summary (s) and/or analyses may be provided if deemed necessary.

#### 4.2.2 Definition of Baseline, Month 6 and Month 12

Baseline lipid measurements are defined as the average of the pre-dose measurement on Day 1 and all measurements from the Qualification Period. If the Day 1 pre-dose and Qualification Period measurements are all missing, then the last non-missing measurement from the Screening Period will be used as baseline. For lipids other than TG, missing baseline values will be imputed using the multiple imputation method described in Section 4.9.1.4 in the SAP. Note that if on Day 1, there are multiple pre-dose assessments, then the last assessment with non-missing value will be used as the Day 1 pre-dose assessment.

The baseline for platelet is defined as the average of all assessments prior to the first dose of Study Drug.

The baseline for other measurements is defined as the last non-missing assessment prior to the first dose of Study Drug.

The Month 6 lipid assessments are defined as the average of non-missing Weeks 25 and 27 fasting assessments. The Month 12 lipid assessments are defined as the average of non-missing Weeks 51 and 53 fasting assessments. For both Month 6 and Month 12, if 1 of the 2 assessments is missing, then the other non-missing assessment will be used.

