### **1.2.4. Safety and Tolerability Endpoints**

Safety and tolerability assessments include: adverse events, vital signs and weight, physical examinations, clinical laboratory tests, electrocardiogram (ECG), and use of concomitant medications. Safety and tolerability results in patients receiving olezarsen will be compared with those receiving placebo.

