### 10.3 Populations

Full Analysis Set: All patients who are randomized and received any amount of Study Drug (olezarsen or placebo). The FAS represents the practically-feasible intent-to-treat (ITT) population as delineated in ICH Guideline E9. This population will be used for the primary analysis of efficacy.

Per Protocol Set (PPS): Subset of the FAS who received at least 5 monthly doses of Study Drug within the first 6 months of the Treatment Period, have a baseline fasting TG assessment, and who have no significant protocol deviations that could compromise the interpretation of efficacy. Significant deviations will be determined prior to unblinding for statistical analysis. This population will be used for supportive inferences concerning efficacy.

Safety Set: All patients who are randomized and receive any amount of Study Drug. This population will be used for all safety analyses.

PK Population: All patients who are randomized and receive any amount of olezarsen and have at least 1 evaluable concentration result post-first dose. This population will be used for analysis of PK data.

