### 4.6 Analysis Sets

For purposes of analysis within this SAP, the following populations are defined:

**Full Analysis Set (FAS):** All patients who are randomized and received any amount of Study Drug (olezarsen or placebo). The FAS represents the practically feasible intent-to-treat (ITT) population as delineated in International Conference on Harmonization (ICH) Guideline E9. This set will be used for the primary analysis of efficacy.

**Per Protocol Set (PPS):** Subset of the FAS who received at least 5 monthly doses of Study Drug within the first 6 months of the Treatment Period, have a baseline fasting TG assessment, and who have no significant protocol deviations that could compromise the interpretation of efficacy. Significant protocol deviations will be determined prior to unblinding for statistical analysis. This set will be used for supportive inferences concerning efficacy.

**Safety Set:** All patients who are randomized and received any amount of Study Drug. This set will be used for all safety analyses.

**PK Set:** All patients who are randomized and received any amount of olezarsen and have at least 1 evaluable concentration result post-first dose. This set will be used for analysis of PK data.

The number and percentage of subjects in each analysis set will be summarized by treatment group, total olezarsen treated, and overall based on randomized patients.

A by-subject listing of analysis sets, including the inclusion/exclusion flag for each analysis set and reasons for exclusion from each analysis set, will be provided.

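### Safety tables follow the randomised arm, so a patient given another arm's treatment, should that happen, would be counted under a treatment not received

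*Combined protocol and SAP*

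**What the plan says.** SAP 4.2.1 sets one grouping rule for both kinds of result: "Efficacy and safety results will be summarized under the treatment to which patients are randomized". For safety it then allows for a patient who turns out, after unblinding, to have received a treatment other than the one assigned, and says "such cases will be discussed and noted in footnotes where applicable". Nothing there moves such a patient to another column.

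The Safety Set definitions do not settle the grouping. SAP 4.6 has "All patients who are randomized and received any amount of Study Drug. This set will be used for all safety analyses", and protocol 10.3 has "All patients who are randomized and receive any amount of Study Drug. This population will be used for all safety analyses". Both say who is in the set; neither says under which treatment a patient is counted.

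Elsewhere the wording is by receipt. Protocol 1.2.4, repeated in SAP 3.2.4, states "Safety and tolerability results in patients receiving olezarsen will be compared with those receiving placebo". On the columns, SAP 4.2.1 says "The safety data will be presented by the treatment group and total olezarsen treated".

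The same section defines crude incidence as "the number of patients who experienced at least one event times 100 divided by the total number of patients" and adds "The 95% CI of risk difference in crude incidence rate will be estimated using the unstratified Miettinen-Nurminen (MN) method". Exposure-adjusted rates and their differences are also planned.

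**The concern.** Safety tables are read as a statement about exposure: what happened to people who had the drug, against people who did not. Under the as-randomised rule, a placebo-randomised patient given olezarsen would sit in the placebo numerator and denominator and be missing from the pooled olezarsen column, although exposed. An olezarsen-randomised patient given only placebo would be counted in that pooled column without exposure. A footnote discloses the case but leaves the rate, the risk difference and the interval as they were.

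The plan would also describe the same patient in two ways. SAP 4.6 defines the PK Set by having received olezarsen, so a placebo-randomised patient given olezarsen could be an olezarsen patient in the PK listings and a placebo patient in the safety tables.

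The stake is largest where events are few. The special-interest events in SAP 4.10.2.4 (the platelet-related event, and pre-treatment against hypersensitivity) are to be reported with risk differences and intervals against pooled placebo, and there one or two patients may be all the evidence.

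**Working it through.** The plan gives no figure for this point, so there is none to reproduce. The check has two parts.

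**1. Does any section reassign a misallocated patient?**
- SAP 4.2.1: no; discussion and footnote only.
- SAP 4.6 and protocol 10.3: no as-treated clause.
- SAP 4.10 (safety evaluation): tables by treatment group and pooled olezarsen on the Safety Set; no table by treatment received.
- SAP 4.4.2: significant deviations are identified before unblinding, and results are examined including and excluding the affected data. This removes data; it does not move a patient to another column.

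**2. What is one patient worth?**

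Inputs: about 152 patients, 1:1 to cohort, then 3:1 active to placebo (protocol 3.1, SAP 3.1).
- Per cohort: 152/2 = 76. Active: 76 × 3/4 = 57. Placebo: 76 × 1/4 = 19, so pooled placebo = 2 × 19 = 38.
- One patient in the placebo rate: 1/38 = 2.6 points. One patient in an olezarsen rate: 1/57 = 1.8 points.

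Illustration (assumed, since the documents give neither a misallocation count nor an event rate): one patient randomised to placebo receives 80 mg and has the event. As randomised, the 80 mg comparison has 57 against 38 patients; as received, 58 against 37; with the patient excluded, as SAP 4.4.2 would allow, 57 against 37. The risk difference (RD) is x1/n1 − x2/n2. The Miettinen-Nurminen 95% limits are the values d at which (RD − d)²/V(d) equals the 95th percentile of chi-square with 1 df. Here V(d) = [p1(1−p1)/n1 + p2(1−p2)/n2] × N/(N−1), with p1 and p2 the maximum-likelihood rates under p1 − p2 = d.

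| Other events (80 mg, placebo) | As randomised | RD, points (95% CI) | As received | RD, points (95% CI) | Patient excluded, RD |
|---|---|---|---|---|---|
| 0, 0 | 0/57 vs 1/38 | −2.6 (−13.6 to 3.9) | 1/58 vs 0/37 | +1.7 (−7.8 to 9.2) | 0/57 vs 0/37: 0 |
| 2, 0 | 2/57 vs 1/38 | +0.9 (−10.4 to 9.8) | 3/58 vs 0/37 | +5.2 (−4.5 to 14.2) | 2/57 vs 0/37: +3.5 |
| 5, 2 | 5/57 vs 3/38 | +0.9 (−13.2 to 12.6) | 6/58 vs 2/37 | +4.9 (−8.6 to 16.5) | 5/57 vs 2/37: +3.4 |

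The two groupings differ by 4.4, 4.3 and 4.1 points respectively. In the first row the sign reverses. Every interval includes zero. With no misallocated patient the two groupings are identical.

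**The case against.** The strongest case for leaving the rule alone has four parts.

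- **The case is foreseen and visible.** SAP 4.2.1 requires discussion as well as a footnote. Protocol 9.5.3 sends administration errors to the deviation form. SAP 4.4.2 lists all deviations and tests robustness with and without affected data. SAP 4.10.1 and 4.10.2.2 give by-subject dosing and adverse-event listings, so a reader could regroup one or two patients by hand. This stands as mitigation. It does not correct the main tables: exclusion drops the event instead of placing it, and an error discovered only after unblinding falls outside the SAP 4.4.2 review.
- **There is no contradiction.** A reader might infer that SAP 4.2.1 contradicts protocol 1.2.4 and SAP 3.2.4. Those sections describe the comparison in general terms and are not allocation rules, and the Safety Set definitions are silent. SAP 4.2.1 is the only explicit rule. What remains is a mismatch of wording and purpose.
- **No bias is shown.** A reader might infer that the plan pulls drug-related harm towards no difference. That requires a misallocated patient whose event was caused by the treatment received. The documents show no such patient. With 13 planned doses (protocol 8.1), someone given one wrong dose may have most events during correct treatment.
- **As-received grouping has its own difficulty.** For a patient with mixed exposure, the phrase has no meaning until a rule defines it. Without one, a choice is left open after unblinding that the present rule avoids. This stands, and the fix has to include such a rule.

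**Conclusion.** The point holds as a minor, conditional one. If a patient receives another arm's treatment, the main safety tables will count that patient under a treatment not received, and SAP 4.4.2 softens this without repairing it. At the planned arm sizes one such patient with an event is worth 2.6 points of the placebo rate or 1.8 points of an olezarsen rate. In the constructed examples the risk difference shifts by about 4 points. Its practical weight is for rare events.

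This rests on three assumptions: the planned 57/57/38 are realised, at least one misallocation occurs, and that patient has the event in question. The documents support no statement about how likely that is.

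Nor do they support the broader conclusion that the safety results are biased as planned. With no misallocation the effect is exactly zero. Protocol-allowed reductions from 80 mg to 50 mg are part of the assigned regimen and are not misallocation.

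**What to change.** Amend SAP 4.2.1 as follows.

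1. Keep efficacy as randomised.
2. Tabulate the Safety Set by treatment actually received.
3. Fix a mixed-exposure rule before unblinding. For example: a placebo-randomised patient who received any olezarsen counts as olezarsen-treated, and an olezarsen-randomised patient counts as placebo only if every dose received was placebo. The rule should also say which dose column a reassigned patient enters.
4. Keep protocol-allowed 80-to-50 mg reductions in the 80 mg column for tabulation.
5. List every reassigned patient with the randomised arm, and show event timing relative to the wrong dose.

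The cost is a short paragraph and one extra treatment variable. Dosing details are already recorded (protocol 9.5.3, SAP 4.10.1), so no new data collection is needed. There is one small downside: a patient with only a brief wrong exposure may have events from the correctly treated period moved to another column. The timing in item 5 lets a reader see this. The existing discussion and footnote, and the SAP 4.4.2 check, can stay.
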